Being able to properly diagnosis and monitor SPFN is therefore not only important for patients with idiopathic SFPN to have adequate, earl diagnoses for proper treatment and counseling, but also for patients with established Fabry disease to have good monitoring of SFPN progression and assessment of ERT efficacy and adjunct therapy for pain management.

Differentiating Fabry-induced SFPN from other causes (diabetes, amyloidosis, hereditary neuropathies and other multisystemic genetics and inflammatory/auto-immune disorders) can be clinically challenging early in the disease presentation when only symptoms of SFPN are apparent. Neuropathic pain with an onset in childhood or adolescence and/or chronic pains in the hands and feet exacerbated by changes in outside or body temperature, and decreased cold sensation on examination are strongly suggestive of Fabry disease. This data might however be elusive for years leading to considerable delay in diagnosis¹¹.

In general SFPN is diagnosed through a combination of symptoms, signs and confirmatory diagnostic testing. Nerve conduction studies are not sensitive enough in most of the cases leaving the ankle skin punch biopsy with measurement of intraepidermal nerve fiber density (IENFD) as the main gold standard diagnostic tool. Despite its utility and reproducibility, skin biopsy is invasive, expensive and requires a central laboratory for processing and interpretation.

Sophisticated autonomic function test (AFT) equipment, which includes a quantitative sudomotor axon reflex testing (QSART), is already in use at major medical centers, including MGH, as one of several methods recommended by the American Academy of Neurology for diagnosing SFPN¹². However, full AFT testing takes an hour to complete and requires rigorous preparation to undergo the test.

A new device, Sudoscan™ (Impeto Medical, Paris, France) has been cleared by the FDA as a non-invasive galvanic skin response method to measure sweat gland function. There are no preparations required and the measurement takes about 2 minutes. The Sudoscan device consists of four metal plates on which patients place their hands and feet while standing. A small, low-voltage DC current is applied to the plates, which attracts chloride ions from the sweat glands on the palms of the hands and soles of the feet. The resulting electrochemical skin conductance (ESC) is measured and related to the subject's capacity to sweat. Normative scales of adult sweat function are preloaded in the device and compared to actual measurements to determine if a subject's sweat response is reduced, which is associated with neuropathy. Thus, Sudoscan is marketed as a rapid screening test for SFPN. Several researchers have shown Sudoscan to be useful for detecting early SFPN in diabetic adults, the largest group at risk of SFPN¹³⁻¹⁵, chemotherapy-induced SFPN as well as sudomotor changes in cystic fibrosis (unpublished data). Because much of the focus has been on diabetes, there are no studies to-date of the feasibility of using Sudoscan for screening for other causes of SFPN.

Sudoscan™ is a promising modality to test SFPN in Fabry disease. Defective sweating is one of the hallmarks of Fabry disease and is thought to originate not only from a decrease in nerve fiber density of sweat gland innervation, but also from storage of glycolipids in the sweat glands themselves causing sweat gland dysfunction¹⁶ which might be unique to Fabry disease and contributing to a specific pattern of ESC. Data by the Sudoscan™ manufacturer suggests increased sensitivity with the ability of detecting abnormalities very early in the disease process even when only mild fiber density changes are seen on skin biopsy and long before any significant change can be detected by AFT (unpublished data). This modality; if proven useful in detecting SFPN in Fabry disease could be used not only as a diagnostic tool but also as a monitoring tool to evaluate the effect of ERT and other adjunct therapy.

In the Neuro-genetics unit at the Massachusetts General Hospital (MGH), we also follow hundreds of patients with rare diseases such as mitochondrial disease and connective tissue disorders. Despite the variable pathophysiology of these disorders SFPN seems to be a common pathogenic pathway shared with Fabry disease and leading to the same multiple complaints from the patients. In mitochondrial disease, SFPN is thought to be the result of lack of energy production and abnormal nerve metabolism, whereas in connective tissue disease, the abnormal structural proteins within the tissues are likely the cause. Because of these very different mechanisms and the fact that Sudoscan may be more sensitive to subtle SFPN changes, one might speculate that there are possibly discriminating ESC parameters (intensity, slope and pattern of conductance on the hands and feet) that might be able to distinguish SFPN within these 3 disease groups.

Thus we seek to find faster, less-invasive ways to diagnose and monitor small-fiber polyneuropathy in Fabry disease as well as identify a signature pattern of Fabry-induced SFPN in comparison to other rare diseases. Since Sudoscan measurement is non-invasive and takes only 2 minutes, it is an attractive potential add-on to the routine clinical care of our patients.

Aims:

The aims of this preliminary study are to:

Aim 1.

Analyze electrochemical skin conductance and compare data to SFPN standard of care diagnostic testing (QSRT and skin biopsy) in patients with Fabry disease and evaluate the reliability and sensitivity of SUDOSCAN™ as a new method to assess sweat gland function for the screening of Fabry disease.

Aim 2.

Determine whether there is a specific signature pattern of the ESC (intensity, slope and pattern of conductance on the hands and feet) that distinguishes Fabry disease from other disorders causing SFPN such as mitochondrial disease and connective tissue disorders.

Methods

Study population

Adults and children ages 4 to 65 years recruited at MGH Neurogenetics clinic. If local recruitment is incomplete, advertisement will be made on patient support groups for broader national patients' enrollment. Informed consent will be obtained from all participants prior to the measurement with SUDOSCAN™. Young participants age 17 and below will provide Assent in addition to Consent from their parents.

Submission to the Institutional Review Board (IRB) for this protocol will be initiated once this proposal has been approved.

A. Study groups - Inclusion criteria

-Patients (males and females) with confirmed Fabry disease (by GLA enzymes and/or DNA testing) naïve and on ERT, mitochondrial diseases (electron transport chain and/or DNA testing) and connective tissue diseases (clinical criteria and/or DNA testing when available)

-Consenting adults and children who are old enough to stand with hands and feet on the Sudoscan plates for at least 2 minutes.

B. Subject population - Exclusion criteria

- In general we exclude potential subjects with cognitive, psychiatric, or other problems that preclude informed consent.

- Patients with history of glucose intolerance or diabetes.

- Patient on chemotherapy

- Other exclusion criteria are:

- People with any open or bleeding wounds at any sensor plate contact surface location
- People with any type of implantable device
- People with missing hand(s) and/or leg(s)
- Pregnant women or women who are uncertain about a possible pregnancy

Study Design

Aim 1.

Analyze electrochemical skin conductance and compare data to SFPN standard of care diagnostic testing (QSRT and skin biopsy) in patients with Fabry disease and evaluate the reliability and sensitivity of SUDOSCAN™ as a new method to assess sweat gland function for the screening of Fabry disease.

- Thirty patients with Fabry disease will be enrolled. Emphasis will be given to treatment-naïve patients but we expect the majority of the patients to be on ERT. We will proactively seek patients who have been on ERT for a short period of time (less than 1 year) and patients who are on ERT with persistent acroparesthesia to maximize the yield of SFPN findings.

- Patients' charts will be reviewed for pertinent medical history, inclusion/exclusion criteria assessment and demographic data (age, gender, body mass index (BMI)). Medications intake will also be reviewed to eliminate patients who are on neurotoxic drug that might cause neuropathies.

- All subjects will receive a complete neurological examination comprising: the neurological symptom score, cranial nerve function, and an evaluation of muscle weakness, muscular atrophy, bilateral reflexes, and sensory function of upper and lower extremities.

-SUDOSCAN™ will be used on all patients at baseline to collect ESC. A subset of these patients (15) will also undergo standard of care diagnostic testing for SFPN: QSART at the MGH neuromuscular clinic' AFT suit as well as skin biopsy interpreted in [name] [name]'s laboratory. [name] is the director of the neuropathology laboratory and has tremendous expertise in SFPN with normative data for both children and adults¹⁷.

Results of QSRT, skin biopsy and ESC output from SUDOSCAN™ will be compared at baseline.

Aim 2.

Determine whether there is a specific signature pattern of the ESC (intensity, slope and pattern of conductance on the hands and feet) that distinguishes Fabry disease from other disorders causing SFPN such as mitochondrial disease and connective tissue disorders.

- Twenty patients with mitochondrial disease and 15 with connective tissue disease will be enrolled. Patients' charts will be reviewed for pertinent medical history, inclusion/exclusion criteria assessment and demographic data (age, gender, body mass index (BMI)). Medications intake will also be reviewed to eliminate patients who are on neurotoxic drug that might cause neuropathies.

- All subjects will receive a complete neurological examination comprising: the neurological symptom score, cranial nerve function, and an evaluation of muscle weakness, muscular atrophy, bilateral reflexes, and sensory function of upper and lower extremities.

-SUDOSCAN™ will be used on all patients at baseline to collect ESC. A subset of these patients (8 to 10) will also undergo standard of care diagnostic testing for SFPN: QSART at the MGH neuromuscular clinic' AFT suite as well as skin biopsy interpreted in [name] [name]'s laboratory. Results of QSRT, skin biopsy and ESC output from SUDOSCAN™ from each group will be compared to the Fabry patients group to assess for any signature pattern of ESC in Fabry disease.

Study Procedure

1) SUDOSCAN™

Subjects will be studied at MGH at a time convenient to them. No special preparations are required. This study is accomplished in a single session lasting less than 30 minutes including paperwork. Study staff will explain the study and gather informed consent. Subjects will then remove their shoes and socks and stand on two metal plates on the floor while placing the palms of their hands on two metal plates on a table. The plates are connected to the SUDOSCAN™ device. The subject stands still for two minutes while skin conductance data are gathered. There is no perceptible sensation. Results are expressed immediately as Electrochemical Skin Conductance (ESC, μ S) representing the ratio between the current generated and the constant DC stimulus (lower than 4 V) applied on the electrodes. Sudomotor dysfunction is evaluated according to the ESC measured on the limbs: > 60 IS = no dysfunction; 60–40 IS = moderate dysfunction; and < 40 IS = severe dysfunction (normative database on >300 subjects).

The SUDOSCAN™ apparatus is small and can be transported in a small case. This will be available at each clinic and will be used to screen every patient seen in the MGH neurogenetics clinic during their regular clinic visit. Fabry patients who are not regular MGH patients and enrolled for the purpose of this study will be assessed in our research center after full examination and comprehensive medical history is obtained.

There are no risks or discomforts associated with sweat measurement with SUDOSCAN™. The procedure is similar to standing on a digital scale for 2 minutes. The applied voltage is less than or equal to 4V with a current of about 0.2 mA. At this level there is no sensation from contact with the electrode plates. There is no radiation associated with the SUDOSCAN™ device.

2) QSRT

Quantitative sudomotor axon reflex test measures axon reflex-mediated sudomotor responses quantitatively and evaluates postganglionic sudomotor function. The recording is typically performed on the forearm and three lower extremity skin sites to evaluate the distribution of postganglionic deficits. The test has a high sensitivity, specificity and reproducibility. The test is straightforward in established laboratories such as the MGH neuromuscular AFT suite¹⁸. There is no specific risk associated with this procedure.

3) Skin biopsy for intraepidermal nerve fiber density (IENFD)

IENFD and sweat gland nerve fiber (SGNF) density evaluations uses a skin biopsy and immunostaining of the tissue to identify and count the intraepidermal and sudomotor nerve fibers. Assessment of nerve fiber density typically involves a 3-mm punch biopsy of skin from the leg (10 cm above the external malleolus). After sectioning by microtome, the tissue is immunostained with anti-protein-gene-product 9.5 (PGP 9.5) antibodies and examined with immunohistochemical or immunofluorescent methods.

Skin biopsy is a well-tolerated procedure and complications which are very rare include: pain, infection, bleeding and delayed healing with scarring.

Primary endpoints

ESC output from SUDOSCAN™. Normative ESC scales previously obtained by Sudoscan™ are provided by the manufacturer for comparison.

Secondary points

1) Specific Fabry disease ESC signature pattern on SUDOSCAN™ testing comparison to other rare diseases with SFPN.

2) ESC characteristics within the Fabry group with assessment of specific phenotypic features of Fabry disease such as disease severity, kidney and cardiac involvement to evaluate any meaningful correlation between the degree of ESC derangement to the disease severity/progression.

Statistical analysis

For a p value <1% at 99.5 power a sample size of 20 patients is sufficient (taking into account standard deviations and data variation from diabetes studies). Multivariate analysis will be used to uncover any ESC variation correlating with the severity of Fabry disease and the different phenotypic variability of the disease.

Anticipated results

We expect SUDOSCAN™ results to be in accordance with the decrease in total sweat response measured by QSART and skin biopsy small fiber neuropathy low density. We expect to see an improvement of ESC in patients on ERT. We expect to see a specific ESC pattern in patients with Fabry disease as compared to other diseases with SFPN.

Potential benefits to society

We anticipate adding to the body of knowledge about SFPN. This method may in time develop into a clinical diagnostic tool with the potential to supplement or replace more arduous tools such as skin biopsy or AFT.

REFERENCES

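### Aim 1 promises reliability and sensitivity for Fabry screening, but one scan each in 30 known Fabry patients can show only concordance with SFPN tests and a case-only abnormal rate

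*Combined protocol and SAP*

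**What the plan says.** All references are to the combined protocol and SAP.

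- **Aims, and again Study Design, Aim 1.** Beyond comparing ESC with QSART and biopsy, the study is to "evaluate the reliability and sensitivity of SUDOSCAN™ as a new method to assess sweat gland function for the screening of Fabry disease". The list of aims opens with "The aims of this preliminary study are to".
- **Inclusion criteria.** The Fabry group consists of patients "with confirmed Fabry disease (by GLA enzymes and/or DNA testing"), untreated or on ERT.
- **Study Design, Aim 1.** Thirty Fabry patients are enrolled. The plan actively looks for those on ERT for under a year, or with persisting acroparesthesia, so that more SFPN is found. ESC is recorded at baseline. On the reference tests: "A subset of these patients (15) will also undergo standard of care diagnostic testing for SFPN". On the analysis: "Results of QSRT, skin biopsy and ESC output from SUDOSCAN™ will be compared at baseline".
- **Study Design, Aim 2.** "Twenty patients with mitochondrial disease and 15 with connective tissue disease will be enrolled". The background says of these disorders that "SFPN seems to be a common pathogenic pathway shared with Fabry disease".
- **Study Procedure, 1) SUDOSCAN.** There is one session and the result appears at once. ESC limits are given at 60 and 40. The device "will be used to screen every patient seen in the MGH neurogenetics clinic during their regular clinic visit".
- **Statistical analysis.** The section gives a sample size of 20 and a multivariate analysis of ESC against Fabry severity and phenotype. It names no analysis of reliability, sensitivity or screening.

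**The concern.** Aim 1 names two properties, reliability and sensitivity, and one use, screening for Fabry disease. Reliability in the usual measurement sense needs repeated measurements. Screening performance needs people whose Fabry status is unknown when they are scanned and is then verified. The plan describes neither. Its reference tests, QSART and biopsy, establish SFPN rather than Fabry disease.

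What is at stake is the conclusion the study may draw. Good results would show that ESC tracks SFPN tests in known Fabry patients. As Aim 1 is worded, the same results would appear to answer a wider question that the design does not address. Fixing the narrower question before data are collected settles this.

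**Working it through.** **Inputs from the document.** 30 confirmed Fabry patients (Study Design, Aim 1; Inclusion criteria); one baseline scan in one session (Study Design; Study Procedure 1); QSART and biopsy in 15 of the 30 (Study Design, Aim 1); 20 + 15 = 35 comparison patients (Study Design, Aim 2).

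**Assumed inputs.** The document gives no expected sensitivity, number of SFPN-positive patients, correlation, false-positive rate or ICC. All such values below are illustrations.

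**1. The plan's own figure.** Statistical analysis states n = 20 for p < 1% at 99.5 power (read as percent). It gives no effect size, SD, test or sidedness, so it cannot be reproduced. Back-solving under a two-sided normal approximation:
- One sample of 20: d = (2.576 + 2.576)/√20 = 1.15.
- 20 per group: d = 5.152 × √(2/20) = 1.63.

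Neither quantity concerns reliability or sensitivity, so the figure does not support this part of Aim 1.

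**2. Reliability.** With n patients and k occasions, the degrees of freedom for between-occasion variance are n(k − 1). Here that is 30 × (1 − 1) = 0, so test-retest reliability is not estimable.

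A second scan in all 30 would give 30 degrees of freedom. For the one-way ICC with k = 2, F = (1 + r)/(1 − r) on 29 and 30 df:
- r = 0.80: F = 9, 95% CI 0.62 to 0.90.
- r = 0.90: F = 19, 95% CI 0.80 to 0.95.

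**3. Agreement with, and sensitivity for, SFPN (at most 15 patients).** Exact (Clopper-Pearson) limits are the 2.5% quantile of Beta(x, n − x + 1) and the 97.5% quantile of Beta(x + 1, n − x).
- All 15 SFPN-positive, 12 detected: 80%, CI 52% to 96%.
- Only 10 SFPN-positive, 8 detected: 80%, CI 44% to 97%.
- Rank correlation 0.6 between ESC and IENFD, n = 15: Fisher z = 0.693 ± 1.96 × √(1.06/12) = 0.693 ± 0.583, which back-transforms to 0.11 to 0.86.

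**4. Share of known Fabry patients with abnormal ESC (30 patients).** An assumed 24/30 = 80% has an exact CI of 61% to 92%. As a proportion abnormal among confirmed cases, it is a sensitivity for Fabry disease, but for the cases enrolled. Selecting for persistent symptoms pushes it up relative to a screening population. The plan also expects most patients to be on ERT and ERT to improve ESC, which would push the other way, so the net bias cannot be sized from the document.

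**5. Specificity and screening performance.** Two parts of the plan might seem to supply these.
- *The 35 Aim 2 patients.* An assumed 7/35 abnormal has an exact CI of 8% to 37%. This is a false-positive rate against two selected diseases that the background believes share SFPN with Fabry. It does not describe people who would be screened.
- *Scanning of every clinic patient.* No Fabry confirmation and no analysis is attached to those scans.

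No group of unknown Fabry status is therefore planned to be both scanned and verified.

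**The case against.** The strongest replies, and what stands of each:

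- **Reliability may mean concordance.** The word is undefined, and the baseline comparison with QSART and biopsy would meet that reading. This stands: on that reading the defect is one of wording. Test-retest reliability remains unaddressed on any reading.
- **Sensitivity is properly estimated in confirmed cases.** This also stands. A reader might infer that the study can say nothing about sensitivity for Fabry disease; the document does not support that, since the 30 patients do give such a figure. The limit is the kind of cases enrolled.
- **Aim 1 does not promise specificity or predictive value.** True. A reader might go on to calculate how few abnormal scans would be true Fabry cases in a screening population. The document gives no prevalence and no false-positive rate, so such figures would rest entirely on assumption and show no fault in this plan.
- **Detecting Fabry disease is a genuine motive.** The background describes diagnostic delay and the difficulty of separating Fabry-induced SFPN from other causes. It also raises glycolipid storage in sweat glands as a possible Fabry-specific route to abnormal ESC. So screening is not foreign to the document; the design does not deliver it.
- **The study is preliminary, and its stated expectations are modest.** The anticipated results speak of accordance with QSART and biopsy and of a tool that may develop in time. A reader might infer that the results will be misreported as a validated screen; nothing in the document shows that. Its modest expectations sit better with a narrower aim.

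**Conclusion.** The point holds as a mismatch between Aim 1 and its design. Test-retest reliability cannot be estimated (0 degrees of freedom). Specificity and screening performance for Fabry disease cannot be obtained from any part of the plan. What can be obtained is concordance with, and sensitivity for, SFPN in at most 15 patients, and the abnormal share in 30 known, partly symptom-selected Fabry patients. Both are imprecise: about 52% to 96% and 61% to 92% if the observed rate is 80%.

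These conclusions rest on the design and do not depend on the assumed rates; only the interval widths do. The study remains worth running, and a change of wording with a few added sentences is enough.

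**What to change.** 1. **Reword Aim 1** to: *concordance of ESC with, and sensitivity of ESC against, biopsy IENFD and (separately) QSART for SFPN in patients with known Fabry disease, and the proportion of known Fabry patients with abnormal ESC*. Delete the Fabry-screening phrase. The last clause keeps ESC abnormality due to gland storage, which would otherwise count only as disagreement with biopsy.
2. **Replace reliability with concordance.** Optionally repeat the two-minute scan in the same session and report the ICC as short-term repeatability only, not day-to-day stability.
3. **Choose the 15** for QSART and biopsy without regard to the ESC result, which is visible immediately, and report refusals. The plan gives no selection rule at present.
4. **State the analysis.** Use the ESC limits already in Study Procedure 1 with the limb named in advance, and the laboratories' existing normative limits for IENFD and QSART. Give exact 95% CIs alongside a rank correlation.
5. **Label any false-positive rate** in the Aim 2 patients as against mitochondrial and connective tissue disease.

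**Cost.** The primary endpoint and sample size do not change. The claim is narrower, and there is no guarantee of how many of the 15 will be SFPN-positive. The optional repeat adds about 30 × 2 = 60 minutes over the Fabry group. Item 3 needs some care. The plan calls QSART and biopsy standard of care, so selection independent of findings could make biopsy a research procedure for some participants, possibly including children (enrolment is from age 4). The consent pages are not in the copy reviewed, so whether consent already covers this cannot be judged; the investigators should settle it with the IRB.

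### Aim 2 looks for a Fabry ESC signature in one pooled Fabry group expected to be mostly on ERT, so the result cannot by itself support use at diagnosis or screening

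*Combined protocol and SAP*

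**What the plan says.** **Who is in the Fabry group.** The inclusion criteria admit Fabry patients "naïve and on ERT, mitochondrial diseases" and connective tissue diseases. Study Design, Aim 1 sets the size: "Thirty patients with Fabry disease will be enrolled". It then says: "Emphasis will be given to treatment-naïve patients but we expect the majority of the patients to be on ERT". No minimum number of naïve patients is set. Among treated patients, the plan seeks those with less than a year of ERT and "patients who are on ERT with persistent acroparesthesia to maximize the yield of SFPN findings".

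**What is compared.** Aim 2 enrols 20 mitochondrial and 15 connective tissue patients, whose results "will be compared to the Fabry patients group to assess for any signature pattern of ESC in Fabry disease". The features of interest are the intensity, slope and hand-foot pattern of conductance.

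**What the protocol expects of ERT.** Under Anticipated results: "We expect to see an improvement of ESC in patients on ERT". No size is given.

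**What the signature is for.** The background says that separating Fabry-induced SFPN from other causes "can be clinically challenging early in the disease presentation when only symptoms of SFPN are apparent". It suggests that a pattern particular to Fabry disease could arise partly from "storage of glycolipids in the sweat glands themselves causing sweat gland dysfunction". It names a diagnostic use for Sudoscan and also a monitoring use for patients on ERT. Aim 1 adds screening for Fabry disease.

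**What is adjusted for.** The Statistical analysis section plans a multivariate analysis of severity and phenotype within Fabry disease. ERT status is not named there or under Secondary points.

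**The concern.** A patient whose diagnosis is still open is not on ERT. The group from which the signature would be drawn is expected to be mostly on ERT, and the protocol expects that treatment to change the measured variable. The same short section on anticipated results predicts both an ERT effect on ESC and a Fabry-specific ESC pattern, but the plan has no analysis that keeps the two apart.

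What is at stake is the meaning of the Aim 2 result. If a pattern is found, the reader cannot tell whether it belongs to Fabry disease, to Fabry disease under ERT, or to the particular treated patients who were sought. If none is found, the reader cannot tell whether untreated patients would have shown one.

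**Working it through.** **1. The plan's own figure.** The Statistical analysis section gives 20 patients for a 1% significance level and 99.5% power. It names no comparison, difference or SD, so the figure cannot be reproduced. Solved backwards for two groups of 20, two-sided, it implies a standardised difference of (2.576 + 2.576) × √(2/20) = 1.63 SD. The present point does not depend on that figure.

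**2. Number of naïve patients.** A majority of 30 is at least 16 on ERT, which leaves at most 14 naïve if the protocol's expectation holds. The exact share is not given. Assuming 60 to 90% on ERT leaves 30 × 0.40 = 12 down to 30 × 0.10 = 3.

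**3. Precision of each contrast.** The half-width of a 95% interval for a difference in means, in SD units with a common SD, is 1.96 × √(1/n₁ + 1/n₂). The normal quantile is used; a t quantile would give somewhat wider intervals in the smallest groups.

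| Fabry patients in the contrast | v 20 mitochondrial | v 15 connective tissue |
|---|---|---|
| 30 (pooled) | 0.57 | 0.62 |
| 14 naïve (most possible if the majority are on ERT) | 0.68 | 0.73 |
| 12 naïve (60% on ERT, assumed) | 0.72 | 0.76 |
| 3 naïve (90% on ERT, assumed) | 1.21 | 1.24 |

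For example, 14 v 20 gives 1.96 × √(0.0714 + 0.0500) = 1.96 × 0.348 = 0.68.

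**4. How far pooling could move the result.** If ERT shifts mean ESC by δ and a share p is treated, the pooled Fabry mean lies p × δ from the untreated mean. With p from 0.6 to 0.9, that is 0.30 to 0.45 SD for δ = 0.5 SD and 0.60 to 0.90 SD for δ = 1.0 SD. Both values of δ are assumptions. The smaller range lies inside the pooled half-width of 0.57 SD; the larger lies outside it.

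**5. What that could do to power.** Suppose the untreated difference is 1.0 SD, ERT removes half of it, and 16 of 30 are treated (the first two are assumptions). The pooled difference is 1 − (16/30) × 0.5 = 0.73 of the untreated one. Power for 30 v 20 at two-sided 1% is Φ(d/√(1/30 + 1/20) − 2.576). It falls from 81% at d = 1.0 to 49% at d = 0.73.

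**6. Direction.** Steps 4 and 5 treat ERT as a uniform shift in mean ESC and take no account of which treated patients are sought. Patients with short exposure, or with symptoms that persist on ERT, may have improved little, which works against a pull towards normal. The net direction cannot be settled from the documents.

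**The case against.** The strongest case against is about scope. Aim 2 speaks only of distinguishing Fabry disease from other disorders that cause SFPN. It does not say that this is to be done before diagnosis; that use comes from the background and from Aim 1's screening wording. Monitoring under ERT is a stated purpose too, and treated patients are the right ones for it. The study calls itself preliminary, the signature is a secondary point, and the plan makes no explicit claim about untreated patients. All of this stands, and it limits the point to what the result can support.

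Three stronger readings are tempting, and the documents do not support them:

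- **The signature would be one of purely treated disease.** The group is mixed, and the protocol gives emphasis to naïve patients.
- **Pooling must weaken the signature.** The protocol expects improvement on ERT but gives no size, and the treated patients it seeks may pull the other way. A shift in mean ESC bears mainly on intensity. Nothing in the documents shows that ERT changes slope or hand-foot pattern.
- **A study treatment is present in one arm only.** There are no treatment arms. This is a single-session measurement in disease groups, ERT is background care, and the comparators' treatments are not described.

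It can also be said that a naïve contrast may be too imprecise to use. With 3 naïve patients that would be so, which is why the fix includes a fallback.

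**Conclusion.** The gap is real. As written, Aim 2 yields a contrast between each comparator and a mixed, mostly treated Fabry group. It does not by itself support the diagnostic or screening use that the background and Aim 1 describe, although treated patients remain relevant to monitoring.

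This rests on the protocol's own two expectations: most Fabry patients on ERT, and ESC improved by ERT. The size of the distortion is unknown and its direction uncertain, so the shift and power figures only illustrate one direction under assumed effects. The group sizes are firmer ground: if the expected majority is on ERT, at most 14 of 30 patients can speak to untreated disease. This is a limit on interpretation that is cheap to repair. It does not invalidate the study.

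**What to change.** - Record ERT status and duration for every Fabry patient. The planned review of charts and medications should supply both.
- Report each Aim 2 Fabry-versus-comparator ESC contrast, with its interval, separately for naïve and ERT-treated patients, alongside the pooled contrast.
- Label the pooled contrast as a mixed Fabry group, mostly on ERT.
- Base any statement about distinguishing Fabry disease at diagnosis on the naïve contrast. If naïve patients are too few, limit the Aim 2 conclusion to the mixed or treated group studied.

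This adds no patients and no visits. The cost is the low precision of the naïve contrast, as tabulated above, and possibly a narrower claim.
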